3.5.4 Blinding

Patients themselves, any researchers collecting Health-related Quality of Life data and cardiologists assessing the 4-day ECG results will be unaware of the group to which the patient has been allocated.

The Patient Information Sheet (PIS) will state clearly that the patient will not know whether or not they have had the adjunct maze procedure. However the PIS will also explain that the patient can be un-blinded for medical reasons but that they will still be followed up and remain part of the trial.

Blinding of the patient is essential because the primary outcome is patient benefit. However this is unlikely to be successful if details of the patient's operation are fully accessible in their notes. On the other hand this information must not be held too securely because the patient could be at risk if details are not immediately available if required for medical reasons.

The following strategy will be adopted to accommodate these requirements: Patients' medical notes will be labelled to indicate that they are participating in the Amaze trial. Routine reports will provide details of their elective surgery but will only state that the patient was randomised within the Amaze trial. Notes describing the research intervention (ie the adjunct maze procedure or no trial-related surgery) will be placed in a sealed envelope entitled ' The Amaze Trial ' and kept in the patient's notes. Clinicians will be able to access this information should a medical need arise. The Trial Management Protocol will include details of this ' unblinding protocol '.

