5. OUTCOME MEASURES

5.1 Primary outcomes:

i) Return to SR at 12 months

The number of patients in SR at 12 months after surgery will be determined by 4-day ECG monitors that will be provided for patients to wear continuously for 4 days at 12 months after their operation.

ii) Clinical effectiveness - quality-adjusted survival over 2 years

Clinical effectiveness will be measured by QALYs, which will be calculated by combining length of survival and the EQ-5D (administered at randomisation, on discharge and at 6 weeks and 6, 12 and 24 months after the procedure).

5.2. Secondary outcomes:

- (i) Clinical endpoints of SR at 24 months after surgery, overall survival and stroke-free survival, incidence of anticoagulant-related haemorrhage.
- (ii) Health-related quality of life measured by the EuroQoL, SF-36 & NYHA (for breathlessness)
- (iii) Resource use and cost-effectiveness of the adjunct maze procedure.
- (iv) Anticoagulant and antiarrhythmic drug usage.

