7.2 Economic analysis

An NHS perspective will be adopted for the economic analysis. For both groups patientspecific resource use data will be collected until all patients have completed at least 12months post-randomisation (mean 2 years, maximum 3 years). According to current Department of Health guidelines ⁽¹⁹⁾ an annual discount rate of 3.5% will be applied to all costs incurred between 12 and 24 months post-randomisation. The following resource areas will be measured and valued.

i. Costs of Surgery

The average cost of the initial cardiac surgery will be based on the capital cost of the equipment, variable costs, staff and overhead costs involved. The extra capital cost of the RF ablation device will be annualised and apportioned, where relevant, on a per patient basis. Staff and overhead costs will be allocated according to theatre time and annual patient throughput. The use of variable consumable costs (e.g. blood products, IV heparin) will also be recorded prospectively on a per patient basis.

ii. Costs after surgery

Resource use will be monitored from surgery through to at least 12 months postrandomisation. Information will be collected on hospital admissions due to adverse events including readmissions to hospital, any further cardiac procedures and pacing, GP and outpatient visits and cardiac-related medication. Patients will be asked to record medications taken, inpatient and outpatient visits and any procedures in a purposedesigned questionnaire to be administered alongside the quality of life measures. Patient responses will be validated against hospital and primary care records. Unit costs will be taken from the hospital accounting system for each participating centre and nationally published estimates. ^(20, 21)

iii. Economic outcome measurement

At baseline, on discharge and at 6 weeks, 6 months, 12 months and 24 months post surgery all patients will be asked to complete the EuroQoL questionnaire, including the EQ-5D. The social tariff for the EQ-5D, as estimated by Dolan *et al* will be applied to each patient's self-reported classification in order to calculate utility values.⁽²²⁾ Using actual rather than nominal times of assessment, and assuming a linear change in values between time points, patient-specific utility curves up to 24-months post randomisation will be calculated. A value of zero will be applied at the date of death for those patients who died.

iv. Economic Analysis

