The QALYs experienced by each patient to 24-months post randomisation will be calculated as the area under their utility curve to 24-months or time of death, whichever occurs first. In order to adjust for differences in baseline utilities a linear regression will be fitted to the utilities post treatment, with baseline utility and treatment group as explanatory variables. Treatment effects will be taken from the treatment group coefficient of this regression. For patients who do not complete all EuroQoL/resource use measurements and are censored the methods of Willan and Lin ⁽²³⁾ will be used to estimate mean QALYs and costs.

The incremental cost-effectiveness ratio (ICER), calculated as the ratio of the difference in costs and QALYs, will be estimated using the sample means. In order to generate confidence intervals without assuming any parametric form for the distribution of the costs, bootstrapping will be used to resample patients and repeat the calculations described above 1000 times. ⁽²⁴⁾ Measurements will be summarised as the mean and 95% confidence interval, estimated using bootstrapping. The bootstrap samples for the treatment comparison will also be plotted on the cost-effectiveness plane. In addition, cost-effectiveness acceptability curves (CEAC) for these comparisons will be plotted. The CEAC plots the probability that a functional test is cost-effective if we are willing to pay at most $\pounds X$ per QALY on the vertical axis, against X on the horizontal axis. Sensitivity analysis will be used to explore the impact of the deterministic variables within the economic analysis (e.g. unit cost estimates discount rate).

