Appendix 1. Recruitment and randomisation (at Papworth)

Appendix 2. 07/01/34 The clinical and cost effectiveness of adding an ablation devicebased maze procedure as an adjunct to elective cardiac surgery for patients with pre-existing atrial fibrillation. The Amaze trial (n = 400)

	Baseline	Surgery	6 week visit	6 month	12 months	24 months	Total - new	Total	Total
Month			(routine)	VISIT	VISIT		patients	rollow-ups	episodes
1		ART UP:	Appoint staff,	iocai proje	ect teams, I	SC, DMEC	. Oversee re	gulatory ap	provais all
2	Agree proto	cole Sur	nical & resear	ch staff tr	oining Esta	blich report	ing & monito	ring strated	w Initiato
3	sites		gical & researc	SIT Stall lie	anning. Lota	blishi tepon		ning strateg	ly. Initiate
4	15						15		15
5	16	15					16		16
6	16	16	13				16	13	29
7	20	16	15				20	15	35
8	25	20	15				25	15	40
9	25	25	19				25	19	44
10	25	25	23				25	23	48
11	25	25	24	13			25	37	62
12	18	25	24	15			18	39	57
13	20	18	23	15			20	38	58
14	24	20	19	19	-		24	38	62
15	24	24	18	23	-		24	41	65
16	25	24	24	24			25	48	73
17	24	25	23	24	12		24	59	83
18	25	24	24	23	14		25	61	86
19	24	25	23	19	14		24	56	80
20	24	24	24	18	18		24	60	84
21	25	24	22	24	22		25	68	93
22		25	23	23	23		0	69	69
23			24	24	22		0	70	70
24				23	22		0	45	45
25				24	18		0	42	42
26				22	17		0	39	39
27				23	23		0	46	46
28				24	22			46	46
29					22	12		34	34
30					22	14		36	36
31					23	14		37	37
32					21	18		39	39
33					22	22		44	44
34					23	23		46	46
35						22		22	22
36						22		22	22
37						18		18	18
38						17		17	17
39						23		23	23
40	Primary &	secondar	/ outcome and	lucie & ro	norting	22		22	22
41					porting	22		22	22
42			1117			22		22	22
43						23		23	23
44						21		21	21
45						22		22	22
46						23		23	23
47									
48		Lon	g term analysi	s and rep	orting (not f	unded by H	ITA)		
49									
Totals	400	400	380	380	360	360	400	1480	1880
NOTE:									

352 patients are required for analysis of return to sinus rhythm at 12 months after surgery. 15% drop out is anticipated - this consists of 5% post surgical mortality and an additional 10% failure to provide primary outcome data. To accommodate this attrition we will recruit 400 patients.

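### Appendix 2 shows no primary-analysis period after the last 24-month visits (month 46) although the 2-year QALY is co-primary, and Section 7.2 lets resource-use collection stop short of 24 months

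*Protocol*

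**What the plan says.** **Endpoint.** Protocol Section 5.1 lists as its second primary outcome "Clinical effectiveness - quality-adjusted survival over 2 years". The EQ-5D behind it is "administered at randomisation, on discharge and at 6 weeks and 6, 12 and 24 months after the procedure". Section 7.2 fixes the horizon per patient, with death as the only earlier stop: "The QALYs experienced by each patient to 24-months post randomisation will be calculated as the area under their utility curve to 24-months". Censored patients with incomplete data go to an inverse-weighting method.

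**Timetable.** Appendix 2 is a month-by-month schedule. Its 12-month visits end in month 34. Its 24-month visits run from month 29 to month 46, with 23 in the last month. On the month 40 row the extracted text reads "Primary & secondar / outcome and lucie & ro norting", evidently the label for primary and secondary outcome analysis and reporting. After month 46 the only entry, on the month 48 row, is "Lon g term analysi s and rep orting (not f unded by H ITA", evidently long-term analysis not funded by the HTA. No start month, end month or data cut-off is given for either activity.

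**Resource use.** The opening of Section 7.2 has these data collected until every patient has at least 12 months "post-randomisation (mean 2 years, maximum 3 years". The same section discounts costs incurred between 12 and 24 months, and Appendix 3 schedules resource use at 24 months.

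**Blinding.** Section 3.5.4 says: "Blinding of the patient is essential because the primary outcome is patient benefit". Section 8.6 gives the potentially subjective nature of quality-adjusted survival as the reason.

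**The concern.** An outcome measured to 24 months on each patient cannot be fully analysed before the last 24-month visits are in. The timetable has the primary analysis and reporting label before those visits end and reserves no such period after them. The resource-use rule separately accepts follow-up of 12 months for the latest patients, which is half the horizon of the cost and QALY comparison.

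Nothing in the Protocol makes the analysis wait. Because a censoring method is planned, an early cut could be run without breaking a written rule. The 2-year QALY, the costs and the secondary outcome of SR at 24 months would then rest more heavily on early recruits. There is no scheduled EQ-5D between 12 and 24 months, so a patient censored in that interval contributes survival but no utility for the second year. If comparisons by arm circulated at that stage, some patients would still owe a self-reported EQ-5D in a trial that calls their blinding essential.

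**Working it through.** **1. Reproduce the schedule total.** The 24-month column of Appendix 2, months 29 to 46, is 12+14+14+18+22+23+22+22+18+17+23+22+22+22+23+21+22+23 = 360. This agrees with the totals row, "Totals 400 400 380 380 360 360 400 1480 1880", whose sixth figure is the 24-month column.

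**2. Visits outstanding by assumed cut-off.** Outstanding = 360 minus the cumulative sum of that column.

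| Cut-off, end of month | Done | Outstanding | Share of 360 |
|---|---|---|---|
| 34 | 103 | 257 | 71% |
| 39 | 205 | 155 | 43% |
| 40 | 227 | 133 | 37% |
| 41 | 249 | 111 | 31% |
| 42 | 271 | 89 | 25% |
| 46 | 360 | 0 | 0% |

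**3. Power for the QALY.** Section 3.5.1 gives an SD of 0.3, a difference of 0.083 and a two-sided 5% level. Power = Φ(0.083 / (0.3 × √(2/n)) − 1.96), with n per arm.

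- n = 200: 0.083/0.0300 − 1.96 = 0.807, power 79%. This reproduces the Protocol's approximately 80%.
- n = 180 (all 360 visits): 0.083/0.0316 − 1.96 = 0.665, power 75%.
- n = 135.5 (271 visits, month 42): 0.083/0.0364 − 1.96 = 0.317, power 62%.
- n = 113.5 (227 visits, month 40): 0.083/0.0398 − 1.96 = 0.124, power 55%.

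The step from 79% to 75% is ordinary attrition from 400 to 360. Only the further fall is due to timing. All these figures use only patients with a 24-month visit.

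**4. What the resource-use rule implies.** Randomisation is on the day of surgery (Section 4.1). The surgery column runs over months 5 to 22, and its weighted mean is 5617/400 = month 14.0. With one calendar cut-off for all:

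- a mean of 2 years gives 14.0 + 24 = month 38;
- a maximum of 3 years gives 5 + 36 = month 41;
- a minimum of 12 months gives 22 + 12 = month 34.

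Waiting to month 46 would give a mean of 46 − 14.0 = 32 months and a maximum of 46 − 5 = 41 months, which the stated figures do not match. A fixed 24 months per patient could not produce a 3-year maximum either. The rule therefore reads most naturally as a calendar cut-off near months 38 to 41. This is an inference, and it concerns resource use rather than the EQ-5D.

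**5. Where the analysis block may lie.** The midpoint of months 35 to 46 is 40.5, close to the printed label. The midpoint of months 47 to 49 is 48, exactly where the long-term label sits. The first label may thus be centred in a merged block over months 35 to 46. On that reading the block still ends in the month of the last 23 visits, with no time for data return, cleaning, lock or reporting.

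**The case against.** The strongest reply is that the label's position is an artefact of a damaged table and fixes no date. That stands. A reader might infer that the analysis is set for months 40 to 42 and that up to 37% of patients would lack 24-month data. The documents do not support this: no cut-off is stated, all 360 visits remain scheduled, and the block may run through month 46. Nor is 37% an upper bound. It is 133 of 360 visits (33% of the 400 recruited) under a single assumed cut-off.

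It is also fair that the sections defining the QALY give one horizon, 24 months, and that no text says to analyse whatever is available. Section 7.1 calls 12-month SR the intermediate primary outcome, so work on it may properly begin after month 34. The power figures ignore partial data. Patients without a 24-month visit at the end of month 40 were operated on in months 17 to 22, so they would have 18 to 23 months of survival follow-up and a 12-month EQ-5D already due.

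Early release of results is not stated anywhere. Aggregate results would not reveal an individual's allocation, which stays in a sealed envelope. The blinding risk is therefore conditional.

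Section 10 asks for the final report within 3 months of trial completion. If completion meant the last 24-month visit, that would be months 47 to 49. But completion is undefined, and those are the months Appendix 2 gives only to unfunded long-term work, so the section does not settle the timing.

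Lock procedures often sit in an analysis plan, which is not shown here. The point is not that a procedure is missing but that the Protocol's own timetable and resource-use rule do not fit its co-primary outcome.

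**Conclusion.** The inconsistency is real and should be corrected. On any reading of Appendix 2, primary and secondary analysis and reporting is shown only before month 47, while the last 24-month visits fall in month 46. Section 7.2 separately permits resource-use follow-up of 12 months for the latest patients, against a 24-month cost and QALY comparison and a 24-month collection point in Appendix 3.

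The size cannot be fixed from the documents. For assumed cut-offs between months 39 and 42, 43% to 25% of the scheduled 24-month visits would be outstanding; if the analysis waits for month 46, none would. Complete-case power of 55% (month 40) or 62% (month 42), against 75% with all 360, is a worst case that assumes the Protocol's SD and difference and no recovery from weighting. The documents do not show that data will be lost or that results will be released early. They show a schedule and a collection rule that would allow either.

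**What to change.** 1. In Appendix 2, place the data lock and the comparative analysis of the 2-year QALY, costs and 24-month SR after the last 24-month visit in month 46, and give the reporting period its own months.
2. In Section 7.2, replace the 12-month minimum with collection of resource use to 24 months, or death, for every patient, in line with Appendix 3.
3. State in Section 7.1 that no comparison by arm, including 12-month SR, is released outside the DMEC until the last patient's 24-month EQ-5D is in.

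Cost: the report comes a few months later, and the sponsor must reconcile the reporting period with the unfunded label on months 47 to 49, which is a budget question as well as one of wording. No extra patients or visits are needed, because all 24-month visits are already scheduled.

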7. STATISTICAL & ECONOMIC ANALYSES

7.1 Statistical analysis

All statistical analyses and reporting will comply with CONSORT guidelines ⁽¹³⁾ where possible. For the intermediate primary outcome, return to SR at 12 months, all patients with 4-day ECG results at 12 months will be included in the analysis according to the group to which they were randomised. Secondary analyses will consider a Complier Average Causal Effect analysis ⁽¹⁸⁾ and assessment of sensitivity of results to a range of assumptions regarding missing data. Results will be summarised as the number and percentage in SR and compared using Likelihood Ratio Tests. QALYs will be estimated from serial measurements of the EQ-5D for each patient up to 2 years using interpolation (see economic analysis below).

Secondary outcome measurements will be analysed in a similar way to the above, but will include only those patients for whom measurements were available. Time to all cause death will be explored using Kaplan-Meier curves. Health related quality of life scores and the EQ-5D utility score will be compared using Likelihood Ratio Tests from linear regression models including baseline levels and treatment group.

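### The baseline adjustment is fitted to post-treatment utilities, so no baseline-adjusted effect is specified for the co-primary QALY outcome or for the ICER

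*Protocol*

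**What the plan says.** Protocol section 5.1 makes 2-year QALYs a primary outcome alongside return to sinus rhythm, and section 3.5.1 powers them on a difference of 0.083. Section 7.1 says that "QALYs will be estimated from serial measurements of the EQ-5D for each patient up to 2 years using interpolation" and refers forward to the economic analysis. It names no QALY comparison of its own.

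Section 7.2 iv then gives, in this order:

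- the QALY, "calculated as the area under their utility curve to 24-months or time of death, whichever occurs first";
- the baseline adjustment: "a linear regression will be fitted to the utilities post treatment, with baseline utility and treatment group as explanatory variables";
- the source of the effect: "Treatment effects will be taken from the treatment group coefficient of this regression";
- an inverse-weighting method for mean QALYs and costs in censored patients;
- the ICER, "calculated as the ratio of the difference in costs and QALYs, will be estimated using the sample means";
- confidence intervals, for which "bootstrapping will be used to resample patients and repeat the calculations described above 1000 times".

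Separately, among the secondary outcomes in section 7.1, "the EQ-5D utility score will be compared using Likelihood Ratio Tests from linear regression models including baseline levels and treatment group".

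**The concern.** The QALY definition and the regression do not fit together. The outcome is an area under a curve, in QALYs, but the adjusted model has utilities as its dependent variable, so its coefficient is in utility units. The text also does not say which of the five post-baseline EQ-5D assessments (discharge, 6 weeks, 6, 12 and 24 months) enters the model, or how they are combined. No sentence puts QALYs into a model with baseline utility, and none says that an adjusted coefficient feeds the ICER.

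Two things are at stake. First, the adjusted effect on a co-primary outcome would be reported on a scale that cannot be compared with the 0.083 QALY target. Second, if the ICER uses a raw difference in mean QALYs, it gives up the precision that adjustment offers. Any chance difference in baseline EQ-5D then stays in the denominator, because baseline utility is the first point of each patient's curve and is likely to predict the rest.

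**Working it through.** **Inputs from the Protocol.** Section 3.5.1: 200 per group, difference 0.083 QALYs, SD 0.3, two-sided 5%, incremental cost at most £2,500. Section 4.1: 1:1 allocation. Sections 5.1 and 7.2 iii: EQ-5D at baseline, discharge, 6 weeks, 6, 12 and 24 months.

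**Assumed, because the Protocol does not give them.** Baseline utility SD 0.2 to 0.3; slope 0.4 to 1.0 two-year QALY per unit of baseline utility.

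**1. The plan's own figures.** SE of the QALY difference = 0.3 × √(2/200) = 0.030. 0.083/0.030 − 1.96 = 0.807, which gives power of 79.0%, against a stated value of about 80%. 0.0833 × £30,000 = £2,499, against a stated £2,500. Both reproduce. The power calculation is an unadjusted QALY comparison and this point does not affect it.

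**2. The scale.** A constant utility difference d held for 2 years gives about 2d QALYs, so 0.083 QALYs corresponds to 0.083/2 = 0.0415 in utility. In 4,000 simulated trials per setting (200 per arm, the Protocol's EQ-5D schedule, no deaths or missing data, true constant utility gain 0.0425), the utility regression returned a mean coefficient of 0.043, the QALY regression 0.085, and the raw QALY difference 0.084 to 0.085.

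**3. Raw against adjusted QALY difference.** The gap is the slope times the chance baseline imbalance. SE of the imbalance = SD × √(2/200) = SD × 0.1.

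| Baseline SD | Slope | One-SE imbalance | Shift in QALYs | Share of 0.083 |
|---|---|---|---|---|
| 0.20 | 0.4 | 0.020 | 0.008 | 10% |
| 0.25 | 0.7 | 0.025 | 0.0175 | 21% |
| 0.30 | 1.0 | 0.030 | 0.030 | 36% |

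With the planning SD of 0.3, the shift equals the baseline–QALY correlation times 0.030. The last row needs a correlation of 1.0 × 0.30/0.3 = 1.0, so it is a ceiling. The first row needs 0.4 × 0.20/0.3 = 0.27.

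**4. Simulated gap and precision.** With the correlation parameter at 0.3, 0.5 and 0.7:

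| Quantity | 0.3 | 0.5 | 0.7 |
|---|---|---|---|
| SD of (raw minus adjusted QALY difference) | 0.009 | 0.016 | 0.021 |
| Trials where the two differ by more than a quarter of 0.083 | 3% | 18% | 33% |
| SD of the adjusted estimate | 0.032 | 0.030 | 0.027 |
| SD of the raw estimate | 0.034 | 0.034 | 0.035 |

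**5. On the ICER.** Take £2,500 and an adjusted gain of 0.083: 2,500/0.083 = £30,120 per QALY. The smallest shift gives 2,500/0.091 = £27,500 or 2,500/0.075 = £33,300. The largest gives 2,500/0.113 = £22,100 or 2,500/0.053 = £47,200. For comparison, sampling error in the QALY difference alone, 0.083 ± 1.96 × 0.030 = 0.024 to 0.142, spans about £17,600 (2,500/0.1418) to £103,300 (2,500/0.0242) with cost held fixed.

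**The case against.** The strongest reply is that section 7.2 iv can be read as one sequence: define QALYs, adjust for baseline, take the effect from the adjusted model, form the ICER, then repeat all of this in each resample. On that reading, sample means refers to the original sample as opposed to the bootstrap samples, the adjusted effect already feeds the ICER, and utilities is loose wording for QALYs. This is possible, so a reader who infers that the Protocol definitely prescribes an unadjusted ICER goes further than the text: the word unadjusted does not appear. It does not rescue the regression. Section 7.1 models the EQ-5D utility score separately, so the Protocol uses utility and QALY as distinct terms. If QALYs were meant, the noun still has to be corrected.

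Three other stronger readings are not supported:

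- **Bias.** Under randomisation the raw and adjusted QALY differences estimate the same effect. Only the utility-versus-QALY scale is a genuine difference in quantity.
- **Survival left out of the adjusted effect.** Section 7.2 iii sets utility to zero at the date of death. Whether those zeros enter the regression is not stated, so the omission is unproven.
- **A changed cost-effectiveness conclusion.** At £2,500 the adjusted ICER sits at the £30,000 limit by construction, so any unfavourable shift crosses it. At an assumed £2,000 and baseline SD 0.25, a slope of 1.0 gives 2,000/0.058 = £34,500. That slope implies a correlation of 0.25/0.3 = 0.83. A correlation of 0.5 (slope 0.6, shift 0.015) gives 2,000/0.068 = £29,400, within the range. The crossing depends on the slope chosen.

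It is also fair that the Protocol never itself compares the utility coefficient with 0.083, and that details such as censoring weights within the regression can be left to an analysis plan.

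**Conclusion.** The point holds in a limited form. As written, the Protocol names the wrong dependent variable for the baseline-adjusted analysis of a co-primary outcome, and it specifies no baseline-adjusted QALY effect. This is a matter of what is stated, not of detail left for later. The factor of about two between the scales rests only on a utility difference that is constant over 2 years.

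The ICER part is less certain. An unadjusted QALY difference is the most natural reading but not the only one. If it is what was meant, the cost is chance imbalance and lost precision: 0.008 to 0.030 QALYs for a one-standard-error imbalance under the assumed SDs and slopes, so at most about one standard error of the QALY difference. The sample size is unaffected.

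**What to change.** In section 7.2 iv, replace the post-treatment utilities as the regression outcome with each patient's QALYs to 24 months (utility zero from death), regressed on treatment group and baseline utility. State that this treatment coefficient is both the reported QALY effect and the ICER denominator, and that the regression is refitted in every bootstrap sample. Remove the reference to sample means as it applies to QALYs. The unadjusted ICER may be shown as a sensitivity analysis.

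The cost is about two sentences of analysis wording and minor programming. No new data are needed and the sample size does not change.

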3.5 Recruitment

3.5.1 Sample size

The primary outcome includes a purely clinical end point as well as an outcome of importance to patients.

It consists of: 1) return to sinus rhythm (SR) at 12 months and 2) clinical effectiveness measured as quality-adjusted survival over 2 years. Sample size calculations are based on both these primary endpoints.

1) Return to SR at 12 months.

Published RCTs of ablation as an addition to cardiac surgery have reported rates of return to SR at 12 months ⁽⁸⁻¹²⁾ ranging from 44% to 87% in the trial arms and 5% to 33% in the control arms. If we take a conservative estimate of the difference between the groups (45% vs. 30%) then we would have 80% power to detect this difference with a sample size of 176 in each group, total 352 (2-sided significance 5%). With recruitment of 400 patients this would allow for deaths or loss to follow up at 12 months of approximately 15%.

2) Clinical effectiveness measured as quality-adjusted survival over 2 years.

The emphasis in cost-effectiveness studies is on estimation rather than hypothesis testing so that formal sample size calculations are less important. However, we provide a power calculation based on the effectiveness measure QALY. We could find no studies reporting comparative QALYs in similar patients undergoing ablation and cardiac surgery. From previous studies of patients undergoing angiography for suspected ischaemic heart disease ⁽¹⁶⁾ and patients with refractory angina ⁽¹⁷⁾ the standard deviation of QALYs over 12 and 18 months is at most 0.3. Over follow up of 2 years the minimum clinically important improvement is considered to be one extra month of quality-adjusted life, or 0.083 QALYs. With a sample of 200 patients per group, total 400, we would have approximately 80% power to detect a difference of 0.083 QALYs, (2-sided significance 5%). If the accepted threshold for cost effectiveness were in the range £20-30,000 per QALY and we could demonstrate a significant increase in QALYs of 0.0833, then the procedure would be cost-effective for an incremental cost of at most £2,500.

3.5.2 Feasibility of proposed recruitment:

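### A bootstrap confidence interval for the ICER has limits that cannot be ranked as best and worst value when the QALY difference is not significant, about 1 trial in 5 under the protocol's own planning inputs

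*Protocol*

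**What the plan says.** Protocol section 7.2, part iv (Economic Analysis), gives the estimator: "The incremental cost-effectiveness ratio (ICER), calculated as the ratio of the difference in costs and QALYs, will be estimated using the sample means". The next sentence introduces bootstrapping in order to obtain confidence intervals without a parametric assumption about costs, and says that "bootstrapping will be used to resample patients and repeat the calculations described above 1000 times". Then: "Measurements will be summarised as the mean and 95% confidence interval, estimated using bootstrapping". The same paragraph plans a plot of the resamples on the cost-effectiveness plane and a cost-effectiveness acceptability curve (CEAC). It names no net-benefit scale, no Fieller interval and no rule for resamples whose QALY difference is zero or negative.

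Section 3.5.1 (Sample size) supplies the planning inputs for QALYs. The target gain is "one extra month of quality-adjusted life, or 0.083 QALYs", the variability assumption is that "the standard deviation of QALYs over 12 and 18 months is at most 0.3", and power is stated as about 80% at a two-sided 5% level. That section also remarks: "The emphasis in cost-effectiveness studies is on estimation rather than hypothesis testing". It takes £20,000 to £30,000 per QALY as the threshold range.

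**The concern.** The ICER is the calculation defined immediately before the bootstrap sentence, so an interval for the ratio is the natural reading. A ratio behaves badly when its denominator may be zero. If a material share of resamples has a QALY difference below zero, the ratio passes through infinity inside the central 95% of the bootstrap distribution. Ordering ratios by size then no longer orders them by value for money. A resample in which the maze procedure costs more and yields fewer QALYs has a negative ratio and lands at the low end, where a reader looks for good value.

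Cost-effectiveness is the stated secondary objective (section 2), and 3.5.1 puts the weight on estimation. The interval would be hardest to read when the QALY gain is small or uncertain.

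**Working it through.** **Inputs.** Gain 0.083, SD 0.3, 200 per arm and two-sided 5% come from section 3.5.1. The total of 360 visits at 24 months (180 per arm) comes from the totals row of Appendix 2.

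**Step 1: reproduce the stated power.**
- SE = SD × √(2/n) = 0.3 × √(2/200) = 0.0300.
- Power = Φ(0.083/0.0300 − 1.96) = Φ(0.807) = 79.0%. The protocol says about 80%, so the figure is reproduced.
- Cross-check: 80% power needs 206 per arm by the normal formula, within 3% of 200.

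**Step 2: link significance to the resamples.** The bootstrap distribution of the QALY difference is approximately normal, centred on the estimate d with standard deviation SE. The share of resamples below zero is Φ(−d/SE). It exceeds 2.5% exactly when d/SE < 1.96. Apart from significantly negative estimates, whose probability here is negligible, this is the same as a non-significant QALY difference.

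**Step 3: how often, if the true gain is 0.083.** P = Φ(1.96 − 0.083/SE).

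| Case | SE | P |
|---|---|---|
| 200 per arm | 0.0300 | Φ(−0.807) = 21.0% |
| 200 per arm, gain taken as 1/12 | 0.0300 | Φ(−0.818) = 20.7% |
| 180 per arm | 0.0316 | Φ(−0.665) = 25.3% |
| 200 per arm, baseline adjustment with assumed correlation 0.5 | 0.0300 × √(1 − 0.25) = 0.0260 | Φ(−1.235) = about 11% |

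**Step 4: what happens to the ordering.** An illustration with £2,500, the incremental cost named in 3.5.1, and 0.083 QALYs:

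| Cost difference | QALY difference | ICER | Net benefit at £30,000 per QALY |
|---|---|---|---|
| +£2,500 | +0.083 | 2,500/0.083 = +£30,120 | 2,490 − 2,500 = −£10 |
| +£2,500 | −0.083 | −£30,120 | −2,490 − 2,500 = −£4,990 |
| −£2,500 | +0.083 | −£30,120 | 2,490 + 2,500 = +£4,990 |

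The second row (dominated) and the third (dominant) have the same ICER, and both sort below the first. Net benefit puts all three in the right order.

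**Step 5: simulation.** This used 4,000 trials of 1,000 resamples for each set of inputs, with mean differences drawn from normal distributions. The protocol gives no cost inputs, so the cost difference (£1,000 or £2,500) and cost SD (£2,000 to £10,000) are assumptions, and a percentile interval was assumed.
- Among trials with a non-significant QALY difference, the median share of resamples below zero was about 6% to 7%.
- The lower percentile limit of the ICER was negative in 94% to 99.9% of those trials, over all the assumed cost inputs.
- Overall coverage of the true ratio was about 97%.

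**The case against.** The strongest reply is that the same paragraph already shows the uncertainty validly. The plane shows every resample. The CEAC at £20,000 or £30,000 is the proportion of resamples with positive net benefit at that threshold. Net benefit with an interval therefore adds a magnitude in pounds but no new decision. This stands, and it is why the point is minor. A reader might infer that the plan leaves no valid account of decision uncertainty; the planned plane and CEAC show otherwise.

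Second, the interval sentence speaks of measurements in general and could mean only mean costs and mean QALYs. That reading is possible. But the bootstrap repeats the preceding calculations, of which the ICER is the last, so an ICER interval is the more natural reading. A reader might go further and infer that a bootstrap mean of the ratio is planned. No sentence clearly says so, and the point estimate is explicitly taken from the sample means.

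Third, if the procedure adds cost in essentially every resample, all negative ratios mean dominated and can be ranked as worst. That is right, but the text states no such rule. A separate analysis plan that gave one would remove most of the difficulty.

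Fourth, a reader might infer that the interval has no meaning at all. The simulated coverage of about 97% contradicts that. What fails is the ordering and reading of the limits.

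**Conclusion.** The point holds as a minor one, confined to the ICER interval. Under the protocol's own inputs, the limits would not be readable as best and worst value in about 21% of trials in which the planned gain is real. The figure is about 25% if only the 360 patients seen at 24 months contribute. The 25% leans to the pessimistic side, because deaths still contribute QALYs and censored patients are to be handled by weighting. An SD below 0.3 or a useful baseline adjustment lowers both figures.

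A reader might infer larger frequencies in three ways, none of them supported by the documents:
- Applying the 15% loss noted in Appendix 2. That loss concerns the 12-month rhythm endpoint, and 5 of its 15 points are deaths, which do yield QALYs.
- Taking an SD above 0.3. The protocol gives 0.3 as an upper bound and offers no larger value.
- Taking a true gain well below 0.083. That is a scenario outside the protocol's planning.

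The ICER point estimate, the intervals for the cost and QALY differences, the plane and the CEAC are not affected.

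**What to change.** In section 7.2, part iv:
- Keep the ICER as a point estimate from the sample means, as already written.
- In place of an ICER interval, report incremental net monetary benefit (threshold × QALY difference − cost difference) with a bootstrap 95% confidence interval at £20,000 and £30,000 per QALY, the range in 3.5.1, from the same 1000 resamples.
- Keep the bootstrap intervals for the cost and QALY differences, the plane and the CEAC, and say that these are what the summary sentence refers to.

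Net benefit is linear in both differences, so its interval is well defined whatever the sign of the QALY difference. The cost is a sentence or two of text; no new data or resampling are needed.
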